## Summary of changes

Protocol Section	Change
Protocol Summary	“between February 01 and April 30, 2017” replaced with “February 01 and June 30, 2017”
3 METHODOLOGY 3.1 Summary of Study Design	“The study is to be conducted in 6 investigational sites across Russia with up to 200 patients recruited per site.” replaced with “The study is to be conducted in up to 8 investigational sites across Russia with up to 200 patients recruited per site.” “All patients must have initiated ART between February 01 and April 30, 2017” replaced with “All patients must have initiated ART between February 01 and June 30, 2017”
3 METHODOLOGY 3.3 Inclusion Criteria	“ • Initiated their first-line ART between February 01 and April June 30, 2017” replaced with “ • Initiated their first-line ART between February 01 and June 30, 2017”
5 STUDY PROCEDURES OF DATA COLLECTION 5.3. Retrospective Data Collection	“Data will be retrospectively collected from 6 investigational sites with up to 200 patients recruited per site.” replaced with “Data will be retrospectively collected from up to 8 investigational sites with up to 200 patients recruited per site.”
11 Attachments	Updated External Adverse Event and Product Quality Complaint Form

## List of Abbreviations

---

AE	Adverse event
SAE	Serious adverse event
IRB	Independent Review Board
IEC	Independent Ethics Committee
WHO	World Health Organization
MoH	Ministry of Health
HIV	Human Immunodeficiency Syndrome
AIDS	Acquired Immunodeficiency Syndrome
PLWH	People living with HIV
MSM	Men having sex with men
ART	Antiretroviral therapy
cART	Combined antiretroviral therapy
PI	Protease inhibitors
bPI	Boosted protease inhibitors
NNRTI	Non-nucleoside reverse transcriptase inhibitor
EFV	Efavirenze
ZDV	Zidavudine
TDF	Tenofovir
3TC	Lamivudine
FTC	Emtricitabine
ABC	Abacavir
CV	Cardiovascular
CK	Chronic kidney (disease)
CNS	Central nervous system
CD	Cluster of differentiation
SAR	Serious adverse reaction
NSAR	Non-serious adverse reaction
HOI	Health outcomes of specific interest
MAH	Market authorization holder
PQCs	Product quality complaint
CD	Calendar day
EDC	Electronic data capture
eCRF	Electronic clinical reporting form
CI	Confidentiality interval
SOP	Standard Operating Procedure

---

## PROTOCOL SUMMARY

Title	Retrospective evaluation of treatment durability among treatment-naive HIV-infected individuals initiated first-line ART in Russia
Supplier	Atlant Clinical Ltd
Rationale	Treatment durability is an important factor in HIV disease management since HIV infected individuals need to take ART life-long. To date, there is limited data on treatment durability in HIV infected individuals initiating ART in Russia. Understanding the durability of treatment is essential for improving medical care of patient living with HIV.
Primary Objective	To evaluate the 48 weeks treatment durability among treatment naive HIV-infected individuals determined as a percentage of patients remained on initial therapy
Study Design	A non-interventional retrospective study.
Study Population	Treatment-naive at the time of initiation of ART with NNRTI plus two NRTIs or PI boosted by ritonavir with 2 NRTIs per usual standard of care of the investigator in AIDS clinics of Russia.
Study Duration	Up to 24 months will be dedicated to retrospective data collection and analysis from treatment-naïve HIV-infected patients who initiated their first-line ART between February 01 and June 30, 2017
Exposure and Outcome	Initial ART per usual standard of care in AIDS clinics of Russia: NNRTI plus 2 NRTIs or PI boosted by ritonavir with 2 NRTIs. Treatment durability determined as a percentage of patients continuing their first-line for 48 and 96 weeks without changes (switch or withdrawal) evaluated retrospectively
Statistical Methods	Data will be presented descriptively as follows: the number of observations, mean and standard deviation, median, first and third quartiles, minimum and maximum for continuous variables, and the absolute frequencies and percentage of patients presenting the given feature for qualitative variables. The results on the study endpoints (proportion of patients who remain on first-line ART at 48 and 96 weeks) will be presented with two-sided 95% confidence intervals. Univariate and multivariate logistic regression will be used to study the association between patients' baseline demographic and clinical characteristics and treatment discontinuation status.
Sample Size and Power Calculations	1000 patients. The assumed 1-year (approximately 48 weeks) discontinuation rate, based on published research, is 30% [20] therefore the assumed proportion of patients who remain on the first line ART regimen at 48 weeks is 70%. Inclusion of 1000 patients will allow the estimation of this proportion with 95% CI: Lower bound - 67.2%, Upper bound – 72.8%, Actual width (precision) - 5.7% ( $\pm 2.8\%$ ).
Limitations	In this a retrospective study the quality of the data is important. And the potential issue of missing data is a limitation of the study. Therefore, it is important for the sponsor or designee to monitor data completion and perform quality checks during the study. To minimize missing data, a set of core variables is required to be available at enrollment as part of inclusion criteria.

## 1 Background and Rationale

### 1.1 Background

Human immunodeficiency virus infection and acquired immune deficiency syndrome (HIV/AIDS) is a spectrum of conditions which interfere with increasing the risk of developing common infections such as tuberculosis, as well as other opportunistic infections, and tumors that rarely affect people who have working immune systems.[1] These late symptoms of infection are referred to as acquired immunodeficiency syndrome (AIDS).[2] From the time AIDS was identified in the early 1980s to 2017, the disease has caused an estimated 35 million deaths worldwide.[3] In 2016, about 36.7 million people were living with HIV and it resulted in 1 million deaths.[4] Unlike most countries, Russia's HIV epidemic is growing, with the rate of new infections rising by between 10 and 15% each year. It is estimated that over 250 people become infected with HIV every day. [5, 6] By mid-2017, 1.16 million people had been diagnosed with HIV in Russia. However, this does not equate to the number of people currently living with HIV as it does not account for AIDS-related deaths or people who have HIV but are undiagnosed. Although Russia has collected extensive data on HIV since 1987, official estimates for these measures remain under reported and inconsistent. A 2017 data analysis suggests the numbers of AIDS-related deaths are rising. From January to June 2017, 14,630 AIDS-related deaths were recorded, a 13.5% increase over the previous six-month period. HIV is one of the top 10 causes of premature death in Russia. [7, 8]

Life expectancy of people living with HIV (PLWH) increased substantially with the introduction of combined active antiretroviral therapy (cART) [9]. Consequently, assessing long-term treatment outcomes and regimen durability has become increasingly relevant. Patients still experience treatment modifications and interruptions for reasons that may include virological failure, adverse events, or poor adherence [10, 11]; and treatment modifications or interruptions may be associated with increased costs or adverse clinical outcomes. Efavirenz (EFV) and other NNRTIs are the preferred options for the third component in first antiretroviral regimens (first-line ART) to treat HIV infection, according to the World Health Organization Consolidated Guidelines (WHO) [12] and Russian National cART guidelines [13].

In most clinical trials, before the introduction of integrase strand transfer inhibitors (INSTIs), NNRTIs showed better efficacy or non-inferiority in suppressing HIV replication when compared with other regimens [14–16]. Randomized clinical trials, however, are typically conducted over 48- to 96-week periods and evaluate primarily rates of virological suppression in populations selected with stringent criteria [17]. A recent meta-analysis using pooled data of 29 clinical trials evaluated the risk of death [17], AIDS progression, and treatment discontinuation in ART-naive patients comparing non-nucleoside reverse transcriptase inhibitors (NNRTIs), including Efv-based regimens, with boosted protease inhibitor (bPI)-based regimens, and it showed no statistically significant differences between regimens in any of the individual and combined outcomes.

## 1.2 Rationale

The Russian MoH has recently initiated a national program aimed to increase the proportion of HIV diagnosis and linkage to care of HIV infected individuals. Treatment durability is an important factor in HIV disease management since HIV infected individuals need to take ART for many years. [5] To date, there is limited data on treatment durability in HIV infected individuals initiating ART in Russia. Understanding the durability of treatment is essential for improving patient management in order to achieve the goals set by the Russian MoH and the HIV elimination goals set by the WHO.

According to the robust clinical studies data, there was significant increase of CNS AEs in groups of patients treated with EFV [14]. As with other NNRTIs, drug interactions and a low resistance barrier have to be considered. Novel NNRTIs such as etravirine and rilpivirine were implemented in routine clinical practice in Russia recently and have higher cost which may influence access and therefore durability to this third drug medications.

Observational studies, in contrast to clinical trials, have the potential to offer valuable additional information with respect to real-life settings, such as durability of the regimen over longer periods of time. Cohort studies have evaluated the reasons for change of first-line regimen in the short term [10, 18] and long term [19] and the prevalence of use of different NNRTIs and PIs in first-line [12]. Nevertheless, durability of first-line ART and prognostic factors (either positive or negative) measured in current study, such as the probability of requiring ART switch, may have significant economic and public health relevance. Also durability can be highly influenced by local circumstances. Therefore, in this study, the durability of initial ART will be evaluated according to the third component in a cohort from Russia and association of baseline patient characteristics with treatment durability over a long period of time will be explored.

## 2 Objectives and Hypotheses

### 2.1 Primary Objective

- To evaluate the 48 weeks treatment durability among treatment naive HIV-infected individuals initiated ART (NNRTI, PI) determined as a percentage of patients remained on initial therapy without change of the NNRTI or PI agent

### 2.2 Secondary Objectives

- To evaluate the estimated time on therapy without change of the NNRTI or PI agent at 48 weeks among treatment naive HIV-infected individuals initiated ART (NNRTI, PI)
- To describe baseline clinical and demographic characteristics of treatment naive HIV-infected individuals initiated ART (NNRTI, PI)
- To assess association between clinical and demographic characteristics of patients and treatment durability at 48 weeks

- To evaluate the 96 weeks treatment durability among treatment naive HIV-infected individuals initiated ART (NNRTI, PI) determined as a percentage of patients remained on initial therapy without change of the NNRTI or PI agent
- To evaluate the estimated time on therapy without change of the NNRTI or PI agent at 96 weeks among treatment naive HIV-infected individuals initiated ART (NNRTI, PI)
- To assess association between clinical and demographic characteristics of patients and treatment durability at 96 weeks

## 3 METHODOLOGY

### 3.1 Summary of Study Design

This study is a non-interventional retrospective study. Data from patients who signed informed consent form will be collected through retrospective chart or medical records review. Patients have been receiving treatment and diagnostic procedures according to daily clinical practice conducted by his/her physician. There are no procedures that are required as part of this study.

The study is to be conducted in up to 8 investigational sites across Russia with up to 200 patients recruited per site. Each investigational site will be a dedicated HIV clinic or an HIV department in clinic of infectious diseases. It is planned that the first half of the study population (500 patients) will be enrolled during the first 6-9 months and the second half of the study population (500 patients) during the second 6-9 months of the study.

HIV-infected patients with no experience of therapy at time of initiation of ART with NNRTI plus two NRTIs or PI boosted by ritonavir with 2 NRTIs will be enrolled and followed retrospectively for up to 96 weeks with data collection at the approximate time points of baseline (pre-treatment) and at 48 and 96 weeks after start of treatment.

The following ARV drugs are considered according to the standards of care:

- NNRTIs: efavirenz (EFV), nevirapine (NVP), rilpivirine (RPV), ETR (etravirine) etc.
- PIs: LPV (lopinavir), DRV (darunavir), ATV (atazanavir), FPV (fosamprenavir) etc.

All patients must have initiated ART between February 01 and June 30, 2017. A time window for the retrospective visits at baseline, 48 and 96 weeks is envisaged as approximately  $\pm$  8 weeks.

Patients will be retrospectively screened and selected according to inclusion and exclusion criteria prior to enrollment in each investigational site starting the day of its initiation. The study sites will maintain a list of all screened patients. All patients eligible according to the inclusion/exclusion criteria and after signing the informed consent form are to be consequently enrolled for their demographic and clinical data collection through retrospective chart or medical records review. The enrollment will continue until the recruitment goal is reached.

Baseline and follow-up data will be extracted through retrospective chart or medical records review, if available at each investigational site. No additional interventional tests or medical procedures such as additional blood samples, X-ray or other technical investigations will be performed as a part of this study. If any data element is not available, it will be reported as missing.

At baseline, demographic and clinical data on age, gender, employment status, marital status, substance abuse, HIV diagnosis duration, route of infection, AIDS stage, viral load, CD4 count, concomitant medication, comorbidities (noted diagnosis by physician) are to be collected through retrospective chart or medical records review.

At 48 and 96 weeks of retrospective follow-up, the investigators will assess through the medical records whether the patient was still on treatment with initiated ART (NNRTI, PI) and evaluate the estimated time on therapy without change of the NNRTI or PI agent within the class or without change of the NNRTI or PI agent to a different class.

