### **3.3 Inclusion Criteria**

- Adult patients (>18 years of age) with definite HIV-1 infection based on positive lab test and judgement of treating physician according to standards of care
- Naive to antiretroviral treatment at the time of initiation
- Viral load of >1000 copies/ml at the time of initiation of ART
- Initiated their first-line ART between February 01 and June 30, 2017
- Patients are included, if the third component of their first line ART was either NNRTI or boosted PI plus 2 NRTIs
- Completed follow-up from baseline for at least 96 weeks
- Signed informed consent

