### 4.2 Clinical Variables

The following clinical parameters will be retrospectively recorded at baseline:

- 1) HIV diagnosis duration at baseline (years);
- 2) Route of infection: IV drug use, homosexual (MSM), heterosexual, other;
- 3) HIV stage (if applicable): I-V;
- 4) Baseline viral load (copies/ml);
- 5) Baseline CD4 cells count (cells/µl);
- 6) Concomitant medications at baseline;
  - a. Data will be retrospectively captured on medication given for the treatment for any disorder/disease but HIV/AIDS at baseline

- 7) Comorbidities at baseline: No, Yes – CV disease, diabetes mellitus, CK disease, liver disease, viral hepatitis, pulmonary disease, tuberculosis, CNS disease, psychiatric disorder;
- 8) ART therapy: NNRTI plus two NRTIs; PI boosted by ritonavir with 2 NRTIs.

It should be noted that demographic and clinical variables collected in this non-interventional retrospective study are recommended for daily-practice clinical record keeping for the management of HIV-infection in Russia. Thus, these variables are available for the majority of the HIV-infected patients in regular clinical practice and can be collected within locally applicable legal and ethical framework for non-interventional research.

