### 4.3 Outcomes

#### 4.3.1. Treatment Durability

Treatment durability is determined as a percentage of patients continuing their first-line ART with NNRTI plus 2 NRTIs or PI boosted by ritonavir with 2 NRTIs for 48 and 96 weeks without change of the NNRTI or PI agent (“anchor” or “third agent”) within the class or without change of the NNRTI or PI agent to a different class.

According to the Primary objective, the treatment durability is to be retrospectively evaluated at 48 weeks from the time of initiation.

According to the Exploratory objective, the treatment durability is to be retrospectively evaluated at 96 weeks from the time of initiation.

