#### **7.1.2 Secondary Objectives:**

- Time on therapy (weeks) without change of the NNRTI or PI agent at week 48 from the ART initiation will be presented in Kaplan-Meier plots
- Demographic and clinical characteristics at baseline will be presented descriptively by initial ART regimen (NNRTI or boosted PI plus 2 NRTIs) and overall
- Association between characteristics of patients and treatment durability at 48 weeks will be investigated via:
  - Subgroup analysis: number and percent of patients continuing treatment at 48 weeks will be presented descriptively by demographic and clinical characteristics categorized according to 8.1.4
  - Multivariate logistic regression analysis to identify potential risk factors for discontinuation of initial ART at 48 weeks. Demographic and clinical characteristics categorized according to 8.1.4 will be included into multivariate analysis only if they are found significant in univariate logistic regression analysis. Unadjusted (univariate model) and adjusted (multivariate model) odds ratios will be presented with 95% confidence intervals for the parameters included in each of the analyses.
- Percentage of HIV-infected patients remained on first-line ART at 96 weeks after the start of treatment will be presented descriptively with 95% confidence interval by initial ART regimen (NNRTI or boosted PI plus 2 NRTIs) and overall
- Time on therapy (weeks) without change of the NNRTI or PI agent at week 96 from the ART initiation will be presented in Kaplan-Meier plots
- Association between characteristics of patients and treatment durability at 96 weeks will be investigated via:
  - Subgroup analysis: number and percent of patients continuing treatment at 96 weeks will be presented by demographic and clinical characteristics categorized according to 8.1.4

- Multivariate logistic regression analysis to identify potential risk factors for discontinuation of initial ART at 96 weeks. Demographic and clinical characteristics categorized according to 8.1.3 will be included into multivariate analysis only if they are found significant in univariate logistic regression analysis ( $p<0.1$ ). Unadjusted (univariate model) and adjusted (multivariate model) odds ratios will be presented with 95% confidence intervals for the parameters included in each of the analyses.

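### The ±8-week window is applied to baseline as well as to weeks 48 and 96, so values recorded after ART start can be used as baseline in the secondary analyses

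*Combined protocol and SAP*

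**What the plan says.** Protocol section 3.1 (Summary of Study Design) plans "data collection at the approximate time points of baseline (pre-treatment) and at 48 and 96 weeks after start of treatment". Further down, the same section says: "A time window for the retrospective visits at baseline, 48 and 96 weeks is envisaged as approximately" ±8 weeks. Baseline is named in that sentence on the same footing as the two follow-up visits.

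No other section sets a date limit for baseline values or says which value to take when several fall in the window. Section 4.2 lists the CD4 count with no sampling-date rule and describes concomitant medications as "medication given for the treatment for any disorder/disease but HIV/AIDS at baseline". The Study Procedures table in section 5 says only that items are recorded at baseline. Section 7 contains no definition of baseline.

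One variable has partial protection. Section 3.3 requires "Viral load of >1000 copies/ml at the time of initiation of ART", so a viral load from that time should be in the chart. There is no matching criterion for CD4, medications or comorbidities. For unavailable items, section 3.1 provides: "If any data element is not available, it will be reported as missing".

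The baseline categories in section 7.1.3 feed the subgroup tables. They are also the candidate covariates in section 7.1.2 for the "Multivariate logistic regression analysis to identify potential risk factors for discontinuation of initial ART at 48 weeks" and for the matching week-96 model.

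**The concern.** With ART start as time zero, half of a ±8-week baseline window (8 of 16 weeks) lies inside the follow-up period. A site that has no CD4 count from before treatment but has one from week 4 could record it as baseline or report it as missing, and either choice fits the text. With up to 8 sites abstracting charts, practice may differ between them.

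Three things follow for the association analyses:

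- A CD4 count that has risen on treatment can place a patient in too high a category.
- A predictor can be measured after the event it is meant to predict, if the patient had already stopped or switched the agent.
- A diagnosis or medication that arose because of ART can be counted as a baseline risk factor for stopping ART. Section 1.2 reports more CNS adverse events with efavirenz, while section 7.1.3 lists CNS disease, psychiatric disorder and the number of concomitant medications as baseline categories. This route is reverse causation rather than noise. The documents give no figures from which to size it.

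**Working it through.** **Plan's own figure.** Section 7.3 assumes 70% on first-line ART at 48 weeks with N = 1,000. The Wald half-width is 1.96 × √(0.70 × 0.30 / 1,000) = 0.0284, giving 67.2% to 72.8% as stated. Baseline covariates do not enter this estimate, so the baseline window cannot change it.

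**Assumptions for the rest.** From the plan: 30% discontinuation by week 48 (7.3) and the CD4 categories (7.1.3). Not in the documents, and assumed here:

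- a share f = 5%, 10% or 20% of charts supplies an on-treatment value
- the draw is uniform over weeks 0-8
- the CD4 rise d is 25, 50 or 100 cells
- 20% of patients are in each of the five CD4 categories, evenly spread within each
- time to discontinuation is Weibull with shape k = 1, 0.75 or 0.5

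**Step 1: baseline value taken after stopping.** S(t) = 0.7^((t/48)^k). The mean of 1 − S(t) over weeks 0-8 is 2.91%, 5.15% and 9.20% for k = 1, 0.75 and 0.5. Multiplying by 1,000 × f:

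| f | k = 1 | k = 0.75 | k = 0.5 |
|---|---|---|---|
| 5% | 1.5 | 2.6 | 4.6 |
| 10% | 2.9 | 5.1 | 9.2 |
| 20% | 5.8 | 10.3 | 18.4 |

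The range is about 1.5 to 18 per 1,000.

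**Step 2: wrong CD4 category.** The categories <50, 50-100, 101-200 and 201-350 span 50, 51, 100 and 150 cells. The share moved up is min(1, d/width). For d = 50 the shares are 1.00, 0.98, 0.50 and 0.33, which sum to 2.814. Misplaced per 1,000 = 1,000 × f × 0.2 × 2.814 = 28, 56 and 113 for f = 5%, 10% and 20%. The same formula gives 14-56 for d = 25 (sum 1.407) and 37-147 for d = 100 (sum 3.667).

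**Step 3: effect on CD4 odds ratios.** Let the true log odds ratio fall evenly from ln 2 (<50) to 0 (>350), with 30% discontinuing overall. The risks are then 37.5% in <50, 29.7% in 101-200, 26.3% in 201-350 and 23.0% in >350. Take >350 as 351-700.

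Example with f = 20%, d = 50:

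- The >350 group gains 0.20 × 0.333 × 200 = 13.3 patients from 201-350.
- Its risk becomes (46.09 + 3.50) / 213.3 = 23.2%, odds 0.303.
- The <50 group only loses patients, so its odds stay at 0.599.
- Observed odds ratio: 0.599 / 0.303 = 1.98.

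| f | d | True 2.00 (<50 vs >350) reads | True 1.41 (101-200 vs >350) reads |
|---|---|---|---|
| 5% | 50 | 1.99 | 1.42 |
| 5% | 100 | 1.99 | 1.44 |
| 20% | 50 | 1.98 | 1.44 |
| 20% | 100 | 1.96 | 1.51 |

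If patients who have already stopped show no rise, a true 1.00 (<50 vs >350) reads 1.03-1.12 at f = 20%. The top of that range needs d = 100 and k = 0.5.

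**Step 4: sampling error for comparison.** With 200 patients per category, the standard error of the log odds ratio for 2.00 is √(1/74.9 + 1/125.1 + 1/46.1 + 1/153.9) = 0.223, so the 95% interval is about 1.29-3.09. For 1.41 it is about 0.90-2.21. For 1.00 (60 events in each group) it is about 0.65-1.53. Every shift in step 3 lies well inside these intervals.

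**The case against.** The strongest defence is that the text already limits baseline. Section 3.1 calls it pre-treatment, other sections repeat the word baseline, and the window is loosely worded. On an ordinary reading the specific label restrains the general window. This is a reasonable reading, but nothing in the documents says the label prevails. The window sentence is the operational rule, and it names baseline expressly. The ambiguity stands.

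The second defence is size, and it largely succeeds. The analyses affected are secondary, the study tests no formal hypothesis, and the CD4 odds ratios shift by far less than their sampling error. No section shows that any site would in fact use an on-treatment value.

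The third defence concerns the remedy. A fixed 8-week look-back would discard genuine pre-treatment counts taken, say, 10 weeks before the first dose, and complete-case loss could bring its own selection bias. That objection stands and shapes the fix.

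Two stronger readings are tempting and are not supported. A reader might take everyone who stops in weeks 0-8 as affected: 1 − S(8) gives 58, 89 or 136 per 1,000 for k = 1, 0.75 and 0.5, or 19-45% of the 300 expected discontinuations. The harm, however, needs both an on-treatment value and a stop before it was taken, which is the much smaller count in step 1. A reader might also infer that the window blurs the week-48 and week-96 status. Section 4.3.1 already says "the treatment durability is to be retrospectively evaluated at 48 weeks from the time of initiation" and counts week 96 in the same way, so the documents do not support an error in the primary proportion.

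**Conclusion.** The point holds as a gap in the definition of baseline. Section 3.1 gives baseline a two-sided window that conflicts with its own pre-treatment label, and no section closes the half after ART start. CD4, concomitant medications and comorbidities are exposed; viral load is partly protected.

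The numerical consequence is small. The counts of about 1.5-18 per 1,000 (value taken after stopping) and 28-113 per 1,000 (wrong CD4 category, 50-cell rise) rest on assumed chart shares of 5-20%, and on the assumed category split, draw timing and hazard shapes. On those assumptions the CD4 odds ratios are little changed. The reverse-causation route through medications and comorbidities cannot be sized from the documents. A reader might conclude that the association results would be unreliable as a whole; neither the text nor these figures show that. Priority is low, because only secondary analyses are touched.

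**What to change.** In section 3.1, limit the ±8-week window to weeks 48 and 96. Define baseline laboratory values as the last value on or before the day of the first ART dose, and record the sampling date. Do not count concomitant medications or comorbidities first recorded after the first dose as baseline. Let the sponsor choose and state the look-back length, so that genuine pre-treatment values older than 8 weeks need not be lost. Where no qualifying value exists, record it as missing, as section 3.1 already provides, and report the number missing for each variable.

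The edit is a sentence or two. The cost is some additional missing covariates, in a number the documents do not give; section 4.2 says only that "these variables are available for the majority of the HIV-infected patients in regular clinical practice". As an illustration, if 5%, 10% or 20% of patients lack a pre-treatment CD4 count, complete cases in the CD4 model fall from 1,000 to 950, 900 or 800, and expected discontinuations from 300 to 285, 270 or 240. Confidence intervals on the log odds scale widen by √(1/(1 − m)) = 1.026, 1.054 or 1.118, where m is the share missing: about 3%, 5% or 12%. A longer look-back would reduce this loss. The rule is best set before abstraction, since values collected without it may need a second chart review.
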